9 ASSESSMENT OF SAFETY

9.1 Specification of Safety Parameters

9.1.1 *Unanticipated Problem (UaP)*

The Office for Human Research Protections (OHRP) considers unanticipated problems, in general, to include any incident, experience, or outcome that meets all of the following criteria:

1. Unexpected (in terms of nature, severity, or frequency) given (a) the research procedures that are described in the protocol-related documents, such as the IRB-approved research protocol and informed consent document; and (b) the characteristics of the subject population being studied;
2. Related or possibly related to participation in the research (in this guidance document, possibly related means there is a reasonable possibility that the incident, experience, or outcome may have been caused by the procedures involved in the research); and
3. Suggests that the research places subjects or others at a greater risk of harm (including physical, psychological, economic, or social harm) than was previously known or recognized.

If the IRB concurs that an event is an unanticipated problem the IRB will follow the policies and procedures outlined in the University of Michigan Human Research Protection Plan Operations Manual, part 12. (PDF)⁵².

9.1.2 *Adverse Events*

An adverse event is any untoward or unfavorable medical occurrence in a human subject, including any abnormal sign (for example, abnormal physical exam or laboratory finding), symptom, or disease, temporally associated with the subject's participation in the research, whether or not considered related to the subject's participation in the research.

9.1.3 *Serious Adverse Events*

A serious adverse event (SAE) is one that meets one or more of the following criteria:

- Results in death
- Is life-threatening (places the subject at immediate risk of death from the event as it occurred)
- Results in inpatient hospitalization or prolongation of existing hospitalization

- Results in a persistent or significant disability or incapacity
- Results in a congenital anomaly or birth defect
- An important medical event that may not result in death, be life threatening, or require hospitalization may be considered an SAE when, based upon appropriate medical judgment, the event may jeopardize the subject and may require medical or surgical intervention to prevent one of the outcomes listed in this definition.

9.2 Time Period and Frequency for Event Assessment and Follow-Up

Unanticipated problems will be recorded in the data collection system throughout the study.

The PI will record all reportable events with start dates occurring any time after informed consent is obtained until 7 (for non-serious AEs) or 30 days (for SAEs) after the last day of study participation. At each study visit, the investigator will inquire about the occurrence of AE/SAEs since the last visit.

9.3 Characteristics of an Adverse Event

9.3.1 *Relationship to Study Intervention*

To assess relationship of an event to study intervention, the following guidelines are used:

1. Related (Possible, Probable, Definite)
 - a. The event is known to occur with the study intervention.
 - b. There is a temporal relationship between the intervention and event onset.
 - c. The event abates when the intervention is discontinued.
 - d. The event reappears upon a re-challenge with the intervention.
2. Not Related (Unlikely, Not Related)
 - a. There is no temporal relationship between the intervention and event onset.
 - b. An alternate etiology has been established.

9.3.2 *Expectedness of SAEs*

The Study PI will be responsible for determining whether an SAE is expected or unexpected. An adverse event will be considered unexpected if the nature, severity, or

frequency of the event is not consistent with the risk information previously described for the intervention.

9.3.3 **Severity of Event**

The Common Terminology Criteria for Adverse Events (CTCAE) v4.03² scale will be used to grade adverse events:

- Grade 1 Mild; asymptomatic or mild symptoms; clinical or diagnostic observations only; intervention not indicated.
- Grade 2 Moderate; minimal, local or noninvasive intervention indicated; limiting age-appropriate instrumental ADL*.
- Grade 3 Severe or medically significant but not immediately life-threatening; hospitalization or prolongation of hospitalization indicated; disabling; limiting self care ADL**.
- Grade 4 Life-threatening consequences; urgent intervention indicated.
- Grade 5 Death related to AE. A Semi-colon indicates 'or' within the description of the grade. A single dash (-) indicates a grade is not available.

Not all Grades are appropriate for all AEs. Therefore, some AEs are listed with fewer than five options for Grade selection.

Grade 5

Grade 5 (Death) is not appropriate for some AEs and therefore is not an option.

Activities of Daily Living (ADL)

*Instrumental ADL refer to preparing meals, shopping for groceries or clothes, using the telephone, managing money, etc.

**Self-care ADL refer to bathing, dressing and undressing, feeding self, using the toilet, taking medications, and not bedridden.

² https://ctep.cancer.gov/protocolDevelopment/electronic_applications/ctc.htm (Accessed 28Apr2017; Last updated 11/14/16)

9.4 Reporting Procedures

9.4.1 *Unanticipated Problem Reporting to IRB and NIDCR*

Incidents or events that meet the OHRP criteria for unanticipated problems require the creation and completion of an unanticipated problem report form. OHRP recommends that investigators include the following information when reporting an adverse event, or any other incident, experience, or outcome as an unanticipated problem to the IRB:

- appropriate identifying information for the research protocol, such as the title, investigator's name, and the IRB project number;
- a detailed description of the adverse event, incident, experience, or outcome;
- an explanation of the basis for determining that the adverse event, incident, experience, or outcome represents an unanticipated problem;
- a description of any changes to the protocol or other corrective actions that have been taken or are proposed in response to the unanticipated problem.

To satisfy the requirement for prompt reporting, unanticipated problems will be reported using the following timeline:

- Unanticipated problems that are serious adverse events will be reported to the IRB and to NIDCR within 7 calendar days of the problem or of the investigator becoming aware of the event.
- Any other unanticipated problem will be reported to the IRB and to NIDCR within 14 calendar days of the problem or of the investigator becoming aware of the problem.
- If the unanticipated problem involved one or more persons experiencing actual harm, the event will be reported to the IRB as an adverse event.
- If a person did not experience actual harm but an unanticipated problem entailed potential harm, and/or risk of harm to subjects or others, the event will be reported to the IRB as an Other Reportable Information or Occurrence (ORIO).

All unanticipated problems will be reported to NIDCR's centralized reporting system via Rho Product Safety:

- Product Safety Fax Line (US): [name]
- Product Safety Fax Line (International): [contact]
- Product Safety Email: [contact]

General questions about SAE reporting can be directed to the Rho Product Safety Help Line (available 8:00AM – 5:00PM Eastern Time):

- US: [name]
- International: [contact]

9.4.2 *Serious Adverse Event Reporting to the IRB and NIDCR*

Any AE meeting the specified Serious Adverse Event criteria will be submitted on an SAE form to NIDCR's centralized safety system via Rho Product Safety. This report may be sent by fax or email. Once submitted, Rho Product Safety will send a confirmation email to the investigator within 1 business day. The investigator should contact Rho Product Safety if this confirmation is not received. This process applies to both initial and follow-up SAE reports.

SAE Reporting Contact Information:

- Product Safety Fax Line (US): [name]
- Product Safety Fax Line (International): [contact]
- Product Safety Email: [contact]

General questions about SAE reporting can be directed to the Rho Product Safety Help Line (available 8:00AM – 5:00PM Eastern Time):

- US: [name]
- International: [contact]

The study clinician will complete a Serious Adverse Event Form and submit via fax or email to NIDCR via Rho Product Safety within the following timelines:

- All deaths and immediately life-threatening events, whether related or unrelated, will be recorded on the Serious Adverse Event Form and submitted to Product Safety within 24 hours of site awareness.
- Serious adverse events other than death and immediately life-threatening events, regardless of relationship, will be reported by fax within 72 hours of site awareness.

All SAEs will be followed until resolution or stabilization.

The study clinician will report SAEs to the IRB in the Adverse Event form via eResearch system within the following timelines:

- All deaths and life-threatening outcomes that are related and unexpected should be submitted as soon as possible, but within 7 calendar days of site awareness.
- Serious adverse events other than death and life-threatening outcomes that are related and unexpected should be submitted within 14 calendar days of site awareness.
- Serious adverse events that are unrelated and expected should be submitted within 14 calendar days of site awareness.
- All other unrelated and unexpected events should be submitted in aggregate form in conjunction with completion of the scheduled continuing review.

9.4.3 *Reporting of UaPs and SAEs to NIDCR*

A copy of all SAE reports will be provided in a timely fashion to NIDCR/Rho Inc (see Section 9.4.2 for details).

Any UaP must be reported by the investigator to NIDCR/Rho Inc and the reviewing Institutional Review Board (IRB) as soon as possible but no later than 7 calendar days after the investigator first learns of the effect. NIDCR, the Investigator, and Rho Product Safety shall immediately conduct an evaluation of any reported SAE to determine whether it meets UaP reportable criteria. If they determine that a UaP presents an unreasonable risk to subjects, then NIDCR and the Investigator shall terminate all investigations or parts of investigations presenting that risk as soon as possible. Termination shall occur no later than 5 working days after this determination is made and no later than 15 working days after Rho first receives notice of the effect.

9.4.4 *Reporting of Pregnancy*

Any pregnancy occurring after consent has been signed until the subject has completed the protocol will be reported to UM IRBMED and will be reported according to all other applicable procedures in Section 9. This includes following the pregnancy through outcome.

9.5 Halting Rules

If we see a pattern of worsening in symptoms across patients including severe levels on pain measures, we will halt the study to guarantee the safety of all patients.

10 STUDY OVERSIGHT

In addition to the PI's responsibility for oversight, study oversight will be under the direction of a Data and Safety Monitoring Board (DSMB) composed of members with expertise in neuromodulation, neuroimaging and neurology. The DSMB will meet at least annually to assess safety and efficacy data, study progress, and data integrity for the study. If safety concerns arise, more frequent meetings may be held. The DSMB will operate under the rules of a NIDCR-approved charter that will be approved at the organizational meeting of the DSMB. At this time, most data elements that the DSMB needs to assess will be clearly defined. The DSMB will provide recommendations to the NIDCR.

11 CLINICAL SITE MONITORING

Clinical site monitoring is conducted to ensure that the rights of human subjects are protected, that the study is implemented in accordance with the protocol and/or other operating procedures, and that the quality and integrity of study data and data collection methods are maintained. Monitoring for this study will be performed by NIDCR's Clinical Research Operations and Management Support (CROMS) contractor. The monitor will evaluate study processes and documentation based on NIDCR standards and the International Conference on Harmonisation (ICH), E6: Good Clinical Practice guidelines (GCP).

Details of clinical site monitoring will be documented in a Clinical Monitoring Plan (CMP) developed by the CROMS contractor, in collaboration with the NIDCR Office of Clinical Trials and Operations Management (OCTOM) and the NIDCR Program Official. The CMP will specify the frequency of monitoring, monitoring procedures, the level of clinical site monitoring activities (e.g., the percentage of subject data to be reviewed), and the distribution of monitoring reports. Some monitoring activities may be performed remotely, while others will take place at the study site(s). Staff from the CROMS contractor will conduct monitoring activities and provide reports of the findings and associated action items in accordance with the details described in the CMP. Documentation of monitoring activities and findings will be provided to the site study team, the study PIs, OCTOM, and the NIDCR. The NIDCR reserves the right to conduct independent audits as necessary.

12 STATISTICAL CONSIDERATIONS

Intent-to-treat Population: An intent-to-treat analysis will be performed including all subjects who complete at least 1 set of post-treatment assessments following HD-tDCS treatment for the primary and secondary effectiveness objectives of the study.

Safety Population: Safety measures will be reported for all subjects who receive at least 1 session of sham or active HD-tDCS treatment.

Healthy Volunteers: An analysis will be performed including all subjects who complete 1 set of PET sessions. TMD patients will be compared with healthy controls to test for differences in μ OR BP_{ND} at the baseline level in the thalamus and other pain-related regions.

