7.2 TMD Patients

Prescreening (Study Week -8)

Chronic TMD subjects interested in the study will be prescreened via a phone interview using an IRB-approved checklist.

Screening
(*Study Week -3*)

The activities assigned to the Screening Visit will be completed within 3 weeks prior to the first session of Week 1. Following the informed consent process, subjects will undergo a baseline assessment and the completion of questionnaires, as listed in the study schedule (Table 2). The baseline visit will include a medical/dental history with limited physical that involves clinician assessed DC/TMD (Diagnostic Criteria/Temporomandibular Disorder) status. Also covered are a comprehensive medication history (6 months) and a review of eligibility.

Baseline PET/MRI
(*Study Week -1*)

Within 7 days preceding randomization and the first study treatment, subjects will undergo an MRI, as well as a PET scan that uses an [¹¹C]carfentanil radioligand, with a masseter muscle pain challenge via a 5% hypertonic saline intramuscular infusion. Pain questionnaires will also be completed during this visit window. All procedures are targeted for the week prior to HD-tDCS; however, due to occasional scheduling difficulties, they may be completed within 14 days prior to Day 1 of HD-tDCS. Completion of all procedures may require more than one clinic visit.

Treatment HD-tDCS
(*Study Weeks 1 through 2*)

Beginning at Day 1 of HD-tDCS, subjects will be randomized to active treatment or sham procedure. They will then attend 10 sessions, 1 each weekday (Monday through Friday) over a 2-week period, and will receive either the M1 HD-tDCS treatment or the sham treatment, preceded and followed by questionnaires. Missed days can be doubled and/or rescheduled within the 2-week schedule, as necessary, with study team approval.

Follow-up PET
Follow-up MRI &
First Follow-up Visit
(*Study Week 3*)

Within 7 days following the last study treatment, subjects will undergo an MRI as well as a PET scan that uses an [¹¹C]carfentanil radioligand with a masseter muscle pain challenge via a 5% hypertonic saline intramuscular infusion. Pain questionnaires will also be completed during this visit window. All procedures are targeted for the week following completion of HD-tDCS; however, due to occasional scheduling difficulties, they may be completed within 14 days following Day 10 of HD-tDCS. Completion of all procedures may require more than one clinic visit.

Follow-Up #2 & #3
(Study Weeks 6 and 10)

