Pain questionnaires will be completed again at 4 weeks (Follow-Up #2) and 8 weeks (Follow-Up #3) after the final treatment day (Study Weeks 6 and 10, respectively).

Table 2

SCHEDULE OF EVENTS – I. Procedures

Procedures	Phone PreScreening	Screening	PET/MRI #1 (Baseline) ^{1,2}	HD-tDCS #1-10 ⁸	PET/MRI #2/ Follow-up #1 ^{1,2}	Follow-up #2	Follow-up #3	Early Termination ³
Visit	P	1	2	3A-J	4	5	6	ET
Study Week	-8	-3	-1	1 – 2	3	6 (1 mth)	10 (2 mths)	N/A
Prescreening Script/Checklist	X ⁵							
Informed Consent		X ⁵						
Adverse Events		X ⁵	X ⁵	X	X	X	X	X
Medical/Dental History and Physical		X ⁵						
Medication History/ Concomitant Medications		X ⁵	X ⁵	X	X	X	X	
Quantitative Sensory Testing (QST)			X ⁵		X			
Eligibility Assessment ⁴		X ⁵						
PET Scan 
 Pregnancy Test (Dip)⁷ Drug Screen⁷ Blood sample for biomarkers Masseteric Pain Challenge (5% hypertonic saline) 			X ⁵		X			
Blood sample for genetic testing			X ⁵					
MRI Scan			X ⁵		X			
RANDOMIZATION				Week 1				
HD-tDCS (M-F for 2 weeks)				X ⁶				

¹ Target dates for PET/MRI are the week prior to Day 1 HD-tDCS session (Baseline) and the week after completion of HD-tDCS sessions (Follow-up); an additional week window is allowed to account for scheduling issues.

² Procedures may require more than one clinic visit.

³ Applicable if subject completes an in-person visit.

⁴ If subject is deemed eligible, schedule subject visits and provide subject with instructions for PET & MRI.

⁵ Healthy Volunteer subjects complete only these procedures indicated.

⁶ Missed days can be doubled in the (M-F) x 2 schedule, with study team approval. See Section 7.

⁷ Completed within 24 hours prior to PET session

⁸ HD-tDCS sessions will be scheduled M-F. See Section 7.2.

Table 2
SCHEDULE OF EVENTS – II. Questionnaires

Questionnaires	Phone PreScreening	Screening	PET/MRI #1 (Baseline) ^{1,2}	HD-tDCS #1-10 ⁸	PET/MRI #2/ Follow Up#1 ^{1,2}	Follow Up #2	Follow Up #3	Early Termination ³
Visit	P	1	2	3A-J	4	5	6	ET
Study Week	-8	-3	-1	1 – 2	3	6 (1 mth)	10 (2 mths)	N/A
Demographics		X ⁷						
Beck Depression Inventory		X ⁷						
DC/TMD Examination Form		X ⁷				X	X	
Expectation of Effect VAS		X						
McGill Pain Questionnaire (MPQ) (Long Form)		X						
MPQ (Short Form) ⁶		X	X	X	X	X	X	
Positive and Negative Affect Schedule (PANAS) ⁶		X ⁷	X ⁷	X	X	X	X	
GeoPain (via mobile device) ⁶		X	X	X	X	X	X	
Visual Analog Scale (VAS) ⁶		X	X	X	X	X	X	
Graded Chronic Pain Scale		X			X	X	X	

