Brief Pain Inventory (BPI; Short)		X			X	X	X	
Pittsburgh Sleep Quality Index		X ⁷			X	X	X	
PET Subject Information Sheet			X ⁷		X			
tDCS Effects Questionnaire				X	X	X	X	
HD-tDCS Sham/Placebo Assessment				X				
DC for TMD Symptom Questionnaire		X ⁷			X	X	X	

¹ Target dates for PET/MRI are during the week prior to Day 1 HD-tDCS session (Baseline) and during the week after completion of HD-tDCS sessions (Follow-up); an additional week window is allowed to account for scheduling issues. The "Magnetic Resonance (MR) Safety Screening Form" is completed prior to each MRI scan. See Section 2.3.4.

² Procedures may require more than one clinic visit.

³ Applicable if subject completes an in-person visit.

⁴ If subject is deemed eligible, schedule subject visits and provide subject with instructions for PET & MRI.

⁵ Missed days can be doubled in the (M-F) x 2 schedule, with study team approval. See Section 7.

⁶ These assessments will be conducted at Screening, before and after MRI/PET and tDCS Sessions, and at Follow-up visits.

⁷ Questionnaires to be completed by healthy volunteer subjects at the timepoints indicated.

⁸ HD-tDS sessions will be scheduled M-F. See Section 7.2.

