7.3 Withdrawal Visit

If a subject terminates the study early for one of the reasons listed in Section 5.5 or 5.6, and is willing to return to the site for a final study visit, the following will be completed:

- Record adverse events as reported by subject or observed by investigator
- Provide final instructions to subject (e.g., follow-up of ongoing adverse events)

If the subject cannot be reached or is not willing to return to the study site for a final study visit, the subject will be considered lost to follow up.

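### The set called intent-to-treat depends on an undefined, post-randomisation set of assessments, and no pain score is planned at or after withdrawal

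*Combined protocol and SAP*

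**What the plan says.** **The analysis set.** Section 12 gives the population for the primary and secondary effectiveness objectives: "An intent-to-treat analysis will be performed including all subjects who complete at least 1 set of post-treatment assessments following HD-tDCS treatment". Section 7.2 places randomisation before any of these assessments: "Beginning at Day 1 of HD-tDCS, subjects will be randomized to active treatment or sham procedure". The safety population in section 12 requires only one session.

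**The word *set*.** Section 12 uses it once more, for healthy volunteers: "An analysis will be performed including all subjects who complete 1 set of PET sessions". It is not defined for the effectiveness population. Footnote 6 to the questionnaire part of Table 2, which covers the VAS, says: "These assessments will be conducted at Screening, before and after MRI/PET and tDCS Sessions, and at Follow-up visits".

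**Subjects who leave.** The withdrawal visit in 7.3 lists adverse events and final instructions. On anyone who does not attend, it says: "cannot be reached or is not willing to return to the study site for a final study visit, the subject will be considered lost", meaning lost to follow-up. The Early Termination column of Table 2 carries the footnote "Applicable if subject completes an in-person visit" and is marked for adverse events only, with the VAS row blank. An out-of-window visit (7.5) lists adverse events only.

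**The primary time point.** Section 3.2.1 sets it at 4 weeks after completion of the sessions (Follow-Up #2). Section 7.2 says: "Pain questionnaires will be completed again at 4 weeks (Follow-Up #2) and 8 weeks (Follow-Up #3) after the final treatment day".

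**What is deferred.** Section 12.4 leaves the final analysis to a Statistical Analysis Plan. Section 18 lists that plan and the Manual of Procedures as separate from the protocol. Neither is in the text reviewed, and either may define the set.

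**The concern.** An intent-to-treat set keeps subjects in the arm to which they were randomised, whatever happens next. Here membership depends on something that happens after randomisation and that treatment or its side effects could influence. The condition is also open to more than one reading, so the choice could be made after data have been seen.

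Data collection raises a further problem. The primary endpoint is a VAS at Study Week 6, and the plan schedules no pain score once a subject has left. If leaving is related to pain and differs between arms, the comparison of those who remain can be biased in either direction. A later SAP can redefine the set and add missing-data methods, but it cannot recover a VAS that nobody took.

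**Working it through.** **1. The plan's own figure.** Section 12.2 gives 24 evaluable per arm and 20% drop-out: 24 / (1 − 0.20) = 30 per arm, which reproduces the stated number. The allowance is 0.20 × 60 = 12 subjects. It is a planning figure, not a maximum.

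**2. Two readings of *set*.**

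| Reading | Support in the text | Excluded |
|---|---|---|
| A post-session VAS counts | VAS before and after each session (Table 2, footnote 6) | Almost nobody |
| Week 3 visit or later | Section 12 uses *set* for PET sessions; the wording refers to assessments after treatment | Everyone lost before Week 3, with their session VAS |

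**3. A permitted route to loss after treatment.** A positive drug test at a PET visit is an exclusion criterion (5.2). Drug and pregnancy tests before PET #2 are described as assessing eligibility (8.2.1). An investigator may end participation for a newly met exclusion criterion (5.5.1). A subject could therefore complete all 10 sessions and leave in Week 3, before the primary VAS.

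**4. Size of bias under the Week 3 reading.** Let p be the share lost in an arm and d how much worse the leavers' Week 6 change is than the stayers', in SDs. The mean among stayers differs from the full-arm mean by p × d, so

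bias in the difference = pA × dA − pS × dS (A active, S sham; positive favours active).

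This needs all loss to fall before Week 3, leavers to be excluded, and a simple comparison of those measured. Every p and d below is an assumption.

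| Loss, active / sham | d | Bias (SD) |
|---|---|---|
| 20% / 20% | equal in both arms | 0 |
| 25% / 15% | 0.5; 1 | 0.05; 0.10 |
| 30% / 10% | 0.5; 1 | 0.10; 0.20 |
| 10% / 30% | 0.5; 1 | −0.10; −0.20 |
| 20% / 20% | dA = 1, dS = 0 | 0.20 |

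**5. Scale.** The standard error at 24 per arm is √(1/24 + 1/24) = 0.289 SD; at 21 and 27 it is √(1/21 + 1/27) = 0.291 SD. From the noncentral t, biases of 0.05, 0.10 and 0.20 SD move a nominal two-sided 5% error to 5.3%, 6.3% and about 10%.

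**6. What collecting the VAS would gain.** If a share r of leavers is measured at Follow-Up #2 and is representative of leavers, each arm's term becomes d × p × (1 − p)(1 − r) / (1 − p + r × p). For 30% / 10% and d = 1:

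- r = 0: 0.300 − 0.100 = 0.200 SD
- r = 0.5: 0.105/0.85 − 0.045/0.95 = 0.124 − 0.047 = 0.076 SD
- r = 0.8: 0.042/0.94 − 0.018/0.98 = 0.045 − 0.018 = 0.026 SD

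**The case against.** **The set condition may be nearly nominal.** The healthy-volunteer sentence speaks expressly of PET sessions, while the effectiveness sentence speaks of assessments, and section 7.2 has questionnaires after every session. That favours the reading under which almost nobody is excluded. This stands: the two readings need not be equally likely. The wording still does not settle the matter.

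**The planned analysis is a mixed model (12.3.2.1).** VAS recorded before a subject left could enter it, and the bias table would then not apply. If loss were fully explained by recorded VAS and all randomised subjects were in the set, such a model would remove the bias. This also stands in part. Section 12.3.2.1 lists neither the time points nor a missing-data assumption, and the Week 3 reading would discard the very records that the model needs.

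**Redefining the set alone gains little.** A subject with only a Screening VAS adds essentially nothing to the treatment contrast. Agreed: the gain quantified above comes wholly from collecting the VAS, and it assumes that the leavers reached are representative.

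**Stronger readings that the documents do not support.**
- A reader might infer that leavers have no planned pain scores at all. They have those scheduled around each session attended and, if they stay that long, at Week 3. What is absent is a score at or after withdrawal.
- A reader might infer that a positive test before PET #2 forces withdrawal. Section 5.5.1 says only that the investigator may end participation, 2.3.7 allows a repeat drug test, and nothing says that questionnaires then stop.
- A reader might infer that subjects who merely stop sessions are dropped. Section 7.3 concerns subjects who terminate the study, and 7.2 schedules Follow-Up #2 without requiring completed sessions. The silence of 5.5.2, whose heading covers them, is a gap in clarity.

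**Conclusion.** The point holds and should be fixed, with medium confidence. The label does not fit the set, the set is undefined in the text reviewed, and no pain score is planned at or after withdrawal. Followed as written, the plan can exclude randomised subjects and leave the primary VAS uncollected for those who leave.

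The documents do not determine the size of the effect. Exclusions range from almost nobody to everyone lost before Week 3. The illustrative 0.05 to 0.20 SD is conditional on the assumptions in step 4 of the working, and even 0.20 SD is below one standard error. It would be wrong to conclude that the primary result will be biased by that amount, or that 12 subjects will be excluded. The case for acting rests on the data being unrecoverable and the remedy cheap, not on the least favourable row of the table.

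**What to change.** 1. Section 12: define the primary effectiveness set as all randomised TMD subjects, analysed as assigned, with every recorded VAS in the mixed model. If a restricted set is kept, call it modified and define *set*.
2. Sections 7.3 and 7.5 and the Early Termination column: add the VAS, recorded with its actual date. It supplements the Follow-Up #2 value and is not substituted for it.
3. Section 5.5.2: state that stopping sessions or missing PET #2 does not by itself end outcome collection. Seek the Follow-Up #2 VAS on site or remotely unless the subject withdraws consent for further contact, and record the mode.
4. Sections 3.2.1 and 7.2: state which date anchors Follow-Up #2 for subjects who stop sessions early. One section counts from completion of the sessions, the other from the final treatment day. For those who complete all 10 sessions the two agree ("Missed days can be doubled and/or rescheduled within the 2-week schedule, as necessary, with study team approval"). For early stoppers, any anchor other than the last day treated changes the timing stated in 7.2 and should be declared as a change.
5. Add a not-at-random sensitivity analysis if the SAP has none.

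**Cost.** A short amendment needing IRB approval (15.2), with review of the consent form because withdrawn subjects may be contacted; about 12 extra contacts at the planned drop-out; and some VAS values collected in a different mode, whose comparability is untested here. No extra scans are needed, and no stopping, withdrawal or eligibility rule changes.
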